### **Missing month and day**

- If the year of the incomplete stop date is the same as the year of the last dose of study treatment, the month and day of the last dose of study treatment will be assigned to the missing fields
- If the year of the incomplete stop date is before the year of the last dose of study treatment, *December 31* will be assigned to the missing fields
- If the year of the incomplete stop date is after the year of the last dose of study treatment, *January 1* will be assigned to the missing fields

### **Missing month only**

- If only the month is missing, the day will be treated as missing and both the month and the day will be replaced according to the above procedure

### **Missing day only**

- If the month and year of the incomplete stop date are the same as the month and year of the last dose of study treatment, the day of the last dose of study treatment will be assigned to the missing day
- If either the year of the incomplete stop date is before the year of the date of the last dose of study treatment or if both years are the same but the month of the incomplete stop date is before the month of the date of the last dose of study treatment, the last day of the month will be assigned to the missing day
- If either the year of the incomplete stop date is after the year of the date of the last dose of study treatment or if both years are the same but the month of the incomplete stop date is after the month of the date of the last dose of study treatment, the first day of the month will be assigned to the missing day.

## **16.9                   CHARACTER VALUES OF CLINICAL LABORATORY PARAMETERS**

If the reported value of a clinical laboratory parameter cannot be used in a statistical summary table because, for example, the value is a character string rather than a numerical type, a coded value needs to be appropriately determined and used in the statistical analyses. However, the actual values as reported in the database will be presented in data listings.

**Table 16-1 Examples for Coding of Special Character Values for Clinical Laboratory Parameters**

Laboratory Test (Unit)	Possible Lab Results (in SI units)	Coded Value for Analysis
Chemistry: ALT	< 5	0
Chemistry: AST	< 5	0
Chemistry: Bilirubin, Total	< 2	0
Urinalysis: Glucose	= OR > 55, >= 55, > 0	Positive
	<= 0, Negative	Negative
Urinalysis: Ketones	= OR > 8.0, >= 8.0, > 0	Positive
	<= 0, Negative	Negative
Urinalysis: pH	> 8.0, >= 8.0	8.0
	>= 8.5,	8.5
Urinalysis: Protein	= OR > 3.0, >= 3.0, > 0	Positive
	<= 0	Negative

**17.0**

**CHANGES TO ANALYSES SPECIFIED IN PROTOCOL**

[REDACTED]

**18.0**

**SUMMARY OF CHANGES FROM THE ORIGINAL SAP**

[REDACTED]

[REDACTED]

[REDACTED]

[REDACTED]

[REDACTED]

19.0

## **APPENDIX A: JUSTIFICATION FOR NON-INFERIORITY MARGIN**

A high-contrast, black and white image. The left side is dominated by a large, dark, irregular shape, possibly a mask or a heavily processed photograph. The right side features a series of vertical, jagged white lines of varying lengths, creating a textured, abstract pattern. The overall effect is minimalist and graphic.

**20.0**

**APPENDIX B: ATTRIBUTES OF THE ESTIMAND FOR PRIMARY AND SECONDARY ENDPOINTS**

Estimand	Attributes of the Estimands				
	Treatment	Endpoint	Population	Intercurrent Events	Statistical Summary
Primary	Armour Thyroid vs. Synthetic T4	Achievement of Sustained TSH Response	ITT	
IE1: Premature discontinuation of study drug solely due to COVID-19 related reasons
 
IE2: Premature discontinuation of study drug due to other reasons not attributable to COVID-19
 
All data after IE1 or IE2 will be used. Participants who encounter IE1 will be imputed via multiple imputation under the Missing at Random (MAR) mechanism. Participants who encounter IE2 will be imputed as non-responders.
	Stratum-adjusted difference in the percentage of sustained TSH response at end of Titration Period and Stabilization Period, and associated 2-sided 95% confidence interval.
Secondary	Armour Thyroid vs. Synthetic T4	Achievement of titration TSH Response	ITT	
IE1: Premature discontinuation of study drug during the Titration Period solely due to COVID-19 related reasons
 
IE2: Premature discontinuation of study drug during the Titration Period due to other reasons not attributable to COVID-19
 
All data after IE1 or IE2 will be used. Participants who encounter IE1 will be imputed via multiple imputation under the Missing at Random (MAR) mechanism. Participants who encounter IE2 will be imputed as non-responders.
	Stratum-adjusted difference in the percentage of titration TSH response at end of Titration Period, and associated 2-sided 95% confidence interval.

## **21.0**

## **APPENDIX C: THYPRO QUESTIONNAIRE**

### **21.1**

### **SCORING OF THE THYPRO QUESTIONNAIRE**

Each of the 13 ThyPRO scales is scored as a summary score and linearly transformed to range 0-100. This scoring procedure is described step by step below.

#### **Naming of items**

Each item is named TQ{relevant item number}. Item number is indicated left of each item in the questionnaire. Thus, the first item, 'sensation of fullness in the neck' is named TQ1A in the database.

#### **Scoring of responses**

Item responses are scored

0 for 'Not at all'

1 for 'A little'

2 for 'Some'

3 for 'Quite a bit'

4 for 'Very much'

#### **Scale content**

Each scale consists of the following items:

Goitre symptoms scale: TQ1A TQ1B TQ1C TQ1D TQ1E TQ1F TQ1G TQ1H TQ1I TQ1J TQ1K;

Hyperthyroid symptoms scale: TQ1L TQ1M TQ1N TQ1O TQ1P TQ1R TQ1S TQ1T;

Hypothyroid symptoms scale: TQ1Q TQ1CC TQ1DD TQ1EE;

Eye symptoms scale: TQ1U TQ1V TQ1W TQ1X TQ1Y TQ1Z TQ1AA TQ1BB;

Tiredness scale: TQ2A TQ2B TQ2C TQ2D TQ3A TQ3B TQ3C;

Cognitive problems scale: TQ4A TQ4B TQ4C TQ4D TQ4E TQ4F;

Anxiety scale: TQ5A TQ5B TQ5C TQ5D TQ5E TQ5F;

Depressivity scale: TQ6A TQ6B TQ6C TQ6D TQ6E TQ6F TQ6G;

Emotional Susceptibility scale: TQ7A TQ7B TQ7C TQ7D TQ7E TQ7F TQ7G TQ7H TQ7I;

Impaired Social life scale: TQ8A TQ8B TQ8C TQ8D;

Impaired Daily life scale: TQ9A TQ9B TQ9C TQ9D TQ9E TQ9F;

Impaired Sexlife scale: TQ10A TQ10B;

Cosmetic Complaints scale: TQ11A TQ11B TQ11C TQ11D TQ11E TQ11F;

### **Scale scoring**

In principle, scales are scored by simply adding the response values (0-4) for all the items in a scale. Thus, if a patient answered 'Not at all' to all items in the Social impairment scale, the score would be 0; whereas if she answered 'Not at all' to two items, 'A little' to one item and 'Some' to the last item, the score would be 3 (and max score would be 16). However, three additional features expand this procedure: reversal of positively worded items, imputation for individual missing item responses and linear transformation.

Reversal of positively worded items

As part of the scoring procedure, items 3A, 3B, 3C, 6F, 6G, 7H and 7I have to be reversed, i.e. 'Not at all' scored as 4, 'A little' as 3, 'Some' as 2, 'Quite a bit' as 1 and 'Very much' scored as 0.

Scales are transformed linearly to range 0-100 according to the formula

Transformed score=(raw sum score/highest possible raw sum score)\*100.

*Individual missing items will be imputed as follows.* If half or more of the items in a scale is completed, missing items are substituted by the mean of the completed items. Otherwise, total score (or scale) will be set to missing.

For example, the abovementioned patient answering 'Not at all' to two items, 'A little' to one item and 'Some' to the last item, would have a raw score of 3 (0+0+1+2). Highest possible raw score would be 16 (4+4+4+4). The transformed 0-100 score would then be  $3/16*100=19$ .

## 21.2

## SCORING OF THE THYPRO-39 QUESTIONNAIRE

Each of the 13 ThyPRO-39 scales is scored as a summary score and transformed to range 0-100. This scoring procedure is described step by step below.

### Naming of items

Each item is named TQ{relevant item number}. Item number is indicated left of each item in the questionnaire. Thus, the first item, 'sensation of fullness in the neck' is named TQ1A in the database.

### Scoring of responses

Item responses are scored

0 for 'Not at all'

1 for 'A little'

2 for 'Some'

3 for 'Quite a bit'

4 for 'Very much'/'Completely'

### Scale content

Each scale consists of the following items:

Goitre symptoms scale: TQ1A TQ1C TQ1H

Hyperthyroid symptoms scale: TQ1I TQ1M TQ1N TQ1T

Hypothyroid symptoms scale: TQ1Q TQ1CC TQ1DD TQ1EE

Eye symptoms scale: TQ1W TQ1X TQ1BB

Tiredness scale: TQ2A TQ2C TQ3B

Cognitive problems scale: TQ4A TQ4B TQ4F;

Anxiety scale: TQ5B TQ5C TQ5E

Depressivity scale: TQ6A TQ6E TQ6G

Emotional Susceptibility scale: TQ7C TQ7D TQ7H

Impaired Social life scale: TQ8A TQ8B TQ8C

Impaired Daily life scale: TQ9A TQ9C TQ9E

Cosmetic Complaints scale: TQ11A TQ11D TQ11E

Overall QoL: TQ12

Composite scale: TQ2A TQ2C TQ3B TQ4A TQ4B TQ4F TQ5B TQ5C TQ5E TQ6A TQ6E  
TQ6G TQ7C TQ7D TQ7H TQ8A TQ8B TQ8C TQ9A TQ9C TQ9E TQ12

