### **Scoring the individual scales**

The raw scale scores are derived by simply adding the response values (0-4) for all the items in a scale. However, three additional features expand this procedure:

1. reversal of positively worded items,
2. imputation for individual missing item responses and
3. 0-100 transformation.

Reversal of positively worded items

As part of the scoring procedure, items 3B, 6G and 7H have to be reversed, i.e. 'Not at all' scored as 4, 'A little' as 3, 'Some' as 2, 'Quite a bit' as 1 and 'Very much'/'Completely' scored as 0.

Imputation for individual missing items

If half or more of the items in a scale is completed, missing items are substituted by the mean of the completed items.

Linear transformation

All scales (except for the Hypothyroid Symptoms, the Overall QoL scale and the Composite scale, see below) are transformed to range 0-100 according to [Table 21-1](#) below:

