**Table 21-1**

**To the left is the raw score. The corresponding 0-100 score is tabulated for each scale separately. For example, a patient with a raw score on the Goiter Symptoms scale of 6 (e.g. because she answered "Some" to all three Goiter items), will have a 0-100 Goiter Symptoms score of 37. A raw score of 6 on the Tiredness scale, would yield a 0-100 score of 50.**

Raw sum score	Final rescaled short-form score										
	Goiter	Hyper	Eye	Tired	Cognition	Anxiety	Depression	Susceptibility	Social Life	Daily Life	Appearance
0	2	2	1	0	1	1	0	1	0	0	1
1	10	8	8	8	7	10	7	7	8	7	12
2	15	13	14	17	14	18	14	13	17	15	21
3	20	18	20	25	21	26	22	21	25	22	28
4	26	23	25	33	29	34	29	28	33	30	36
5	31	28	32	42	37	41	37	36	42	38	43
6	37	33	38	50	44	49	45	44	50	46	51
7	43	38	45	58	52	56	54	52	58	54	59
8	49	44	52	67	60	63	63	60	67	62	66
9	57	49	60	75	68	71	71	68	75	71	73
10	64	55	68	83	76	79	80	77	83	80	80
11	73	60	78	92	85	87	89	86	92	89	87
12	84	66	89	100	95	96	97	95	100	98	96
13		71									
14		77									
15		84									
16		90									

Transformation of the Hypothyroid Symptoms scale:

The ThyPRO-39 Hypothyroid Symptoms is identical to the original ThyPRO Hypothyroid Symptoms scale and is thus transformed to 0-100 according to the formula

Transformed score=(raw sum score/16)\*100

For example, if a patient answered 'Not at all' to two items, 'A little' to one item and 'Some' to the last item, she would have a raw score of 3 (0+0+1+2). The transformed 0-100 score would then be 3/16\*100=19.

Transformation of the Overall QoL-impact scale/item:

The Overall QoL item (TQ12) is rescaled to 0-100 simply by taking the mean raw score and multiply by 25.

Scoring the Composite scale

The Composite scale is based on the 22 items from the Tiredness, Cognition, Anxiety, Depressivity, Emotional Susceptibility, Impaired Social life Impaired Daily Life and Overall QoL scales:

TQ2A TQ2C TQ3B TQ4A TQ4B TQ4F TQ5B TQ5C TQ5E TQ6A TQ6E TQ6G TQ7C  
TQ7D TQ7H TQ8A TQ8B TQ8C TQ9A TQ9C TQ9E TQ12

The raw score is derived as described above, by summation (with imputation for missing), to range 0-88. The raw score is transformed to 0-100 according to the formula

Transformed score=(raw sum score/88)\*100

21.3

**PATIENT-REPORTED OUTCOMES QUESTIONNAIRES,  
DESCRIPTIONS, AND INSTRUCTIONS – THYPRO  
QUESTIONNAIRE**

Quality of Life Questionnaire  
for Patients with Thyroid Disease

-ThyPROus-

This questionnaire is about how your thyroid disease  
has affected your life.

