Please answer each question by marking  by the  
answer that best fits you. If you are unsure about  
how you want to answer, please give the best answer  
you can.

The first section of the questionnaire is about symptoms, tiredness, memory, mood, and health.

Please base your answers on how you have been feeling in general during the past 4 weeks.

1. *The first questions are about symptoms*

During the past 4 weeks have you	Not at all	A little	Some	Quite a bit	Very much
1a - had the sensation of fullness in the neck?					
1b - had a visible swelling in the front of your neck?					
1c - felt pressure in your throat?					
1d - had pain in the front of your throat?					
1e - had pain in your neck that could be felt in your ears?					
1f - had the sensation of a lump in your throat?					
1g - had the need to clear your throat frequently?					
1h - felt discomfort swallowing?					
1i - had difficulty swallowing?					
1j - had the sensation of suffocating?					
1k - been hoarse?					
1l - had trembling hands?					
1m - had a tendency to sweat a lot?					
1n - experienced palpitations (rapid heart beat)?					
1o - experienced shortness of breath?					
1p - been sensitive to heat?					
1q - been sensitive to cold?					
1r - had an increased appetite?					

During the past 4 weeks have you		Not at all	A little	Some	Quite a bit	Very much
ta	- had loose stools?					
tb	- had an upset stomach?					
tc	- had moist or watery eyes?					
td	- had bags under the eyes or swollen eyelids?					
te	- had the sensation of dryness or "grittiness" in the eyes?					
tx	- had impaired vision?					
ty	- felt pressure in (or behind) the eyes?					
tz	- had double vision?					
taa	- had eye pain?					
tab	- been very sensitive to light?					
tc	- had swollen hands or feet?					

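### SAP 21.2 and 21.1 place ThyPRO item TQ1I in different scales: the short-form hyperthyroid list has TQ1I where the full form has TQ1L (minor inconsistency, conditional on what the source PDF prints)

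*SAP*

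**What the plan says.** SAP Appendix C gives two scoring keys.

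- **Short form (21.2, Scale content):** "Hyperthyroid symptoms scale: TQ1I TQ1M TQ1N TQ1T". The short-form goitre scale there is TQ1A, TQ1C and TQ1H.
- **Full form (21.1, Scale content):** "Hyperthyroid symptoms scale: TQ1L TQ1M TQ1N TQ1O TQ1P TQ1R TQ1S TQ1T" and "Goitre symptoms scale: TQ1A TQ1B TQ1C TQ1D TQ1E TQ1F TQ1G TQ1H TQ1I TQ1J TQ1K".

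Both sections name items in the same way, as TQ plus the questionnaire item number: "Item number is indicated left of each item in the questionnaire". In the questionnaire in SAP 21.3 the two items are "1i - had difficulty swallowing" and "1l - had trembling hands".

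On short-form scoring, 21.2 says: "The raw scale scores are derived by simply adding the response values (0-4) for all the items in a scale". The raw sum is then converted to a 0-100 score through Table 21-1. The SAP equates a short-form scale with its full-form parent in one case only: "The ThyPRO-39 Hypothyroid Symptoms is identical to the original ThyPRO Hypothyroid Symptoms scale".

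**The concern.** The two keys share one naming rule, so TQ1I should mean the same item in both. As the lists read, that item counts towards goitre in the full form and towards hyperthyroid symptoms in the short form. Item 1h, on discomfort swallowing, stays in the short-form goitre scale, so two swallowing items fall in different symptom scales. The item that opens the full hyperthyroid list, trembling hands, is in no short-form scale.

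This matters because the lists are operative scoring rules. A programmer who follows 21.2 literally would add a swallowing item to the hyperthyroid score and leave out trembling hands. The rule that fills a missing item with the mean of the completed ones would also draw on the swallowing item. An item count or range check would not reveal the substitution.

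**Working it through.** **1. Compare the lists.** SAP 21.1 lists 84 distinct codes in 13 scales. SAP 21.2 lists goitre 3, hyperthyroid 4, hypothyroid 4, nine further scales of 3, and TQ12 alone as overall quality of life:

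3 + 4 + 4 + 9 × 3 + 1 = 39.

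Setting TQ12 aside leaves 38 items in the 12 scales common to both sections. Of these, 37 lie in the full scale of the same name. The exception is TQ1I. With TQ1L in its place, all 38 fit.

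**2. Would the SAP's own totals show the letter?**

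- Distinct short-form codes: 39 with TQ1I, 39 with TQ1L.
- Hyperthyroid raw maximum: 4 items × 4 = 16 with either code, matching the last row of the Hyper column in Table 21-1.
- Composite: 22 items × 4 = 88, as the SAP states. It contains neither code.

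Every stated total is reproduced with either letter, so none can show which one the source prints.

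**3. Size of the effect on one person's score.** The Hyper column of Table 21-1, for raw scores 0 to 16, reads:

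2, 8, 13, 18, 23, 28, 33, 38, 44, 49, 55, 60, 66, 71, 77, 84, 90.

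Write H(r) for the entry at raw score r. If the answers to 1i and 1l differ by k and no item is missing, using one item for the other moves the rescaled score by H(r + k) − H(r) in absolute value. Here r is the lower of the two raw sums and runs from 0 to 16 − k.

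| Difference k | Smallest shift | Largest shift |
|---|---|---|
| 0 | 0 | 0 |
| 1 | 5 (13 − 8) | 7 (84 − 77) |
| 2 | 10 (18 − 8) | 13 (90 − 77) |
| 3 | 15 (23 − 8) | 19 (90 − 71) |
| 4 | 20 (28 − 8) | 24 (90 − 66) |

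Example: the other three items sum to 3, item 1l is answered 3 and item 1i is answered 0. Scoring with 1l gives raw 6, rescaled 33. Scoring with 1i gives raw 3, rescaled 18. The shift is 15 points.

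**4. Where the score is used.** The primary and secondary endpoints are based on TSH (SAP 10.1, 10.2). ITT-T3 and Safety-T3 use the hypothyroid scale (SAP 6.2, 6.4), which has the same four items in both keys. SAP 10.4 has no readable content, and SAP 12.0 defers health outcomes to a separate document. No readable analysis is shown to use the short-form hyperthyroid score.

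**The case against.** The whole point rests on one letter in text read from a PDF by program. Three readings of the source are open:

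1. It prints TQ1I, and 21.2 conflicts with 21.1.
2. It prints a lowercase l, so the item is right and only the code is ambiguous.
3. It prints TQ1L, and nothing is wrong.

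The text of this appendix is visibly unreliable. At least 26 questionnaire labels are garbled or truncated: 13 from 1s to 1ee, all 9 in question 7, and 4 in question 8 that have lost their number (13 + 9 + 4 = 26). In several of the first group the digit 1 appears as a t. The codes in the scale lists are all uppercase as read, but that describes the output and does not settle what the source prints. The match of 37 items out of 38 also fits a correct source that was misread. Nor is a mistake wholly hidden: comparing 21.2 with 21.1, in the same appendix, exposes it.

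Most of this stands, and it is why the point is conditional. Two things weigh the other way. The same text keeps TQ1I and TQ1L apart in 21.1, and 1i and 1l apart in 21.3, so these characters were not always confused. And under two of the three readings the SAP needs a correction, a clarification or a note.

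A reader might infer more: that the short-form hyperthyroid score will be computed wrongly, or that a trial result is biased. The documents support neither. They do not show the scoring program. They do not say that every short-form scale must be a subset of its full scale, so the pattern in the lists is an inference and not proof. They also give no answer distributions for 1i and 1l by arm, so no group-level effect can be derived.

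**Conclusion.** The point holds as a minor internal inconsistency, provided the source prints TQ1I. It is a clerical matter and does not challenge the choice of analysis. Its reach is the short-form hyperthyroid score alone; the full ThyPRO scoring and the composite do not change.

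The individual shifts of 5 to 24 points rest on four assumptions: the source prints TQ1I, the instrument's key intends item 1l, the program copied 21.2, and the participant answered the two items differently with no item missing. If any of the first three fails, no score is wrong. Confidence that the SAP itself contains an error is low; the case for checking it does not depend on that confidence.

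**What to change.** - Look at the source SAP to see whether the first hyperthyroid code in 21.2 is a capital I, a lowercase l or a capital L.
- Reconcile 21.2 with 21.1 and the instrument's scoring key. Unless the key shows item 1i, print the code as an unambiguous uppercase TQ1L. If the key does show 1i, add one line saying that this item belongs to a different scale in the full form.
- Confirm that the scoring program reads the item the key specifies.

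The cost is at most a one-character correction or a one-line note, plus one program check. Items 1i and 1l are both in the questionnaire in SAP 21.3, so any affected scores can be recalculated without new data.

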### **Scoring the individual scales**

The raw scale scores are derived by simply adding the response values (0-4) for all the items in a scale. However, three additional features expand this procedure:

1. reversal of positively worded items,
2. imputation for individual missing item responses and
3. 0-100 transformation.

Reversal of positively worded items

As part of the scoring procedure, items 3B, 6G and 7H have to be reversed, i.e. 'Not at all' scored as 4, 'A little' as 3, 'Some' as 2, 'Quite a bit' as 1 and 'Very much'/'Completely' scored as 0.

Imputation for individual missing items

If half or more of the items in a scale is completed, missing items are substituted by the mean of the completed items.

Linear transformation

All scales (except for the Hypothyroid Symptoms, the Overall QoL scale and the Composite scale, see below) are transformed to range 0-100 according to [Table 21-1](#) below:

**Table 21-1**

**To the left is the raw score. The corresponding 0-100 score is tabulated for each scale separately. For example, a patient with a raw score on the Goiter Symptoms scale of 6 (e.g. because she answered "Some" to all three Goiter items), will have a 0-100 Goiter Symptoms score of 37. A raw score of 6 on the Tiredness scale, would yield a 0-100 score of 50.**

Raw sum score	Final rescaled short-form score										
	Goiter	Hyper	Eye	Tired	Cognition	Anxiety	Depression	Susceptibility	Social Life	Daily Life	Appearance
0	2	2	1	0	1	1	0	1	0	0	1
1	10	8	8	8	7	10	7	7	8	7	12
2	15	13	14	17	14	18	14	13	17	15	21
3	20	18	20	25	21	26	22	21	25	22	28
4	26	23	25	33	29	34	29	28	33	30	36
5	31	28	32	42	37	41	37	36	42	38	43
6	37	33	38	50	44	49	45	44	50	46	51
7	43	38	45	58	52	56	54	52	58	54	59
8	49	44	52	67	60	63	63	60	67	62	66
9	57	49	60	75	68	71	71	68	75	71	73
10	64	55	68	83	76	79	80	77	83	80	80
11	73	60	78	92	85	87	89	86	92	89	87
12	84	66	89	100	95	96	97	95	100	98	96
13		71									
14		77									
15		84									
16		90									

Transformation of the Hypothyroid Symptoms scale:

The ThyPRO-39 Hypothyroid Symptoms is identical to the original ThyPRO Hypothyroid Symptoms scale and is thus transformed to 0-100 according to the formula

Transformed score=(raw sum score/16)\*100

For example, if a patient answered 'Not at all' to two items, 'A little' to one item and 'Some' to the last item, she would have a raw score of 3 (0+0+1+2). The transformed 0-100 score would then be 3/16\*100=19.

Transformation of the Overall QoL-impact scale/item:

The Overall QoL item (TQ12) is rescaled to 0-100 simply by taking the mean raw score and multiply by 25.

Scoring the Composite scale

The Composite scale is based on the 22 items from the Tiredness, Cognition, Anxiety, Depressivity, Emotional Susceptibility, Impaired Social life Impaired Daily Life and Overall QoL scales:

TQ2A TQ2C TQ3B TQ4A TQ4B TQ4F TQ5B TQ5C TQ5E TQ6A TQ6E TQ6G TQ7C  
TQ7D TQ7H TQ8A TQ8B TQ8C TQ9A TQ9C TQ9E TQ12

The raw score is derived as described above, by summation (with imputation for missing), to range 0-88. The raw score is transformed to 0-100 according to the formula

Transformed score=(raw sum score/88)\*100

21.3

**PATIENT-REPORTED OUTCOMES QUESTIONNAIRES,  
DESCRIPTIONS, AND INSTRUCTIONS – THYPRO  
QUESTIONNAIRE**

Quality of Life Questionnaire  
for Patients with Thyroid Disease

-ThyPROus-

This questionnaire is about how your thyroid disease  
has affected your life.

Please answer each question by marking  by the  
answer that best fits you. If you are unsure about  
how you want to answer, please give the best answer  
you can.

The first section of the questionnaire is about symptoms, tiredness, memory, mood, and health.

Please base your answers on how you have been feeling in general during the past 4 weeks.

1. *The first questions are about symptoms*

During the past 4 weeks have you	Not at all	A little	Some	Quite a bit	Very much
1a - had the sensation of fullness in the neck?					
1b - had a visible swelling in the front of your neck?					
1c - felt pressure in your throat?					
1d - had pain in the front of your throat?					
1e - had pain in your neck that could be felt in your ears?					
1f - had the sensation of a lump in your throat?					
1g - had the need to clear your throat frequently?					
1h - felt discomfort swallowing?					
1i - had difficulty swallowing?					
1j - had the sensation of suffocating?					
1k - been hoarse?					
1l - had trembling hands?					
1m - had a tendency to sweat a lot?					
1n - experienced palpitations (rapid heart beat)?					
1o - experienced shortness of breath?					
1p - been sensitive to heat?					
1q - been sensitive to cold?					
1r - had an increased appetite?					

During the past 4 weeks have you		Not at all	A little	Some	Quite a bit	Very much
ta	- had loose stools?					
tb	- had an upset stomach?					
tc	- had moist or watery eyes?					
td	- had bags under the eyes or swollen eyelids?					
te	- had the sensation of dryness or "grittiness" in the eyes?					
tx	- had impaired vision?					
ty	- felt pressure in (or behind) the eyes?					
tz	- had double vision?					
taa	- had eye pain?					
tab	- been very sensitive to light?					
tc	- had swollen hands or feet?					
td	- had dry skin?					
te	- had itchy skin?					

2. The following questions are about tiredness

During the past 4 weeks have you		Not at all	A little	Some	Quite a bit	Very much
2a	- been tired?					
2b	- been exhausted?					
2c	- had difficulty getting motivated to do anything at all?					
2d	- felt worn out?					

3. The following questions are about your vitality

During the past 4 weeks have you

	Not at all	A little	Some	Quite a bit	Very much
3a - felt full of life?					
3b - felt energetic?					
3c - been able to cope with the demands of your life?					

4. The following questions are about memory and concentration

During the past 4 weeks have you

	Not at all	A little	Some	Quite a bit	Very much
4a - had difficulty remembering?					
4b - had slow or unclear thinking?					
4c - had difficulty finding the right words?					
4d - been confused?					
4e - had difficulty learning something new?					
4f - had difficulty concentrating?					

5. The following questions are about nervousness and tension

During the past 4 weeks have you	Not at all	A little	Some	Quite a bit	Very much
5a - felt nervous?					
5b - felt afraid or anxious?					
5c - felt tense?					
5d - been concerned about being seriously ill?					
5e - felt uneasy?					
5f - felt restless?					

6. The following questions are about psychological well-being

During the past 4 weeks have you	Not at all	A little	Some	Quite a bit	Very much
6a - felt sad?					
6b - felt depressed?					
6c - felt discouraged?					
6d - cried easily?					
6e - felt unhappy?					

During the past 4 weeks have you	Not at all	A little	Some	Quite a bit	Very much
6f - felt happy?					
6g - had self-confidence?					

7. The following questions are about having difficulty coping or having mood swings

During the past 4 weeks have you	Not at all	A little	Some	Quite a bit	Very much
 - had difficulty coping?					
 - felt "not like yourself"?					
 - noticed you easily felt stressed?					
 - had mood swings?					
 - felt irritable?					
 - felt frustrated?					
 - felt angry?					

	Not at all	A little	Some	Quite a bit	Completely
 - felt in control of your life?					
 - felt in balance?					

The remainder of the questionnaire is about how your thyroid disease may have affected various aspects of your life

8. The following questions are about your relationships with other people

During the past 4 weeks, has your thyroid disease caused you to

Not at all	A little	Some	Quite a bit	Very much
▼	▼	▼	▼	▼

- a. - have difficulty being together with other people (for example, spouse, children, boy/girlfriend, friends, or others)?
- b. - feel you were a burden to other people?
- c. - have conflicts with other people?

During the past 4 weeks have you

Not at all	A little	Some	Quite a bit	Very much
▼	▼	▼	▼	▼

- d. - felt that people in your surroundings have lacked understanding of your thyroid disease?

9. The following questions are about your daily activities

During the past 4 weeks, has your thyroid disease caused you to

	Not at all	A little	Some	Quite a bit	Very much
9a - have difficulty managing your daily life?					
9b - limit your leisure activities or hobbies?					
9c - not be able to participate in life around you?					
9d - have difficulty getting around (for example, walking, running, bicycling, or driving a car)?					
9e - feel as if everything takes longer to do?					

During the past 4 weeks, has your thyroid disease caused you to

I do not work	Not at all	A little	Some	Quite a bit	Very much
9f - have difficulty managing your job (for example, finding it hard to cope or calling in sick)?					

10. The following questions are about your sex life

During the past 4 weeks have you		Not at all	A little	Some	Quite a bit	Very much
10a	- felt your thyroid disease had a negative influence on your sex life?					
10b	- had a decreased sexual desire?					

11. Thyroid diseases (or their treatment) may affect your appearance. (For example, by causing swelling of the neck, swollen face, hands, or feet, or changes in weight or to the eyes.)

During the past 4 weeks,		Not at all	A little	Some	Quite a bit	Very much
11a	- has your thyroid disease affected your appearance (for example, swelling of the neck, eye changes, weight changes)?					
11b	- have you been unsatisfied with your appearance because of your thyroid disease?					
11c	- have you tried to camouflage or mask visible signs of your thyroid disease (for example, by wearing a scarf or sunglasses)?					
11d	- have you been bothered by other people looking at you?					
11e	- has your thyroid disease influenced which clothes you wear?					
11f	- has your thyroid disease made you feel too fat?					

12. *The final question is about to what extent your thyroid disease has affected you overall during the past 4 weeks*

During the past 4 weeks,

Not at all	A little	Some	Quite a bit	Very much
▼	▼	▼	▼	▼

 - has your thyroid disease had a negative effect on your quality of life?

*Please go back and check that you have answered all the questions.*

*Thank you very much for your help answering this questionnaire!*

